### 13.3.1 Primary Analysis

Total study duration is 28 days, with primary analysis performed post baseline (baseline is from Day -7 to Day 0). For primary analysis, average minutes of MVPA on Day 7 will be calculated over all non-missing days between study day 1 (product usage) through 7, inclusive.

Average minutes of MVPA on Day 14 will be calculated over all non-missing days between study day 8 through 14, inclusive. Average minutes of MVPA on Day 21 will be calculated over all non-missing days between study day 15 through 21, inclusive. Any days beyond day 21 will be excluded from all summaries and analyses and will only be present in listed data.

A Mixed Model with Repeated Measures (MMRM) will be used to analyse the change from baseline in MVPA average minutes as the response variable. Subjects will be included as a random effect, and timepoint will be treated as a repeated measure within each subject. If data are found to be non-normal, an appropriate non-parametric test will be performed. If the parameter for the intercept (with compound symmetry structure between visits) is found to be statistically significant ( $p\text{-value} < 0.05$ ), then the individual timepoints (with unstructured covariance structure between visits) will be added as a fixed effect and adjusted means for each timepoint will be presented. P-values and 95% confidence intervals (CIs) for the mean change from baseline in MVPA will be obtained and presented for each timepoint. Other than the global test for an overall change from baseline (i.e., intercept), there will be no other adjustment for multiplicity.

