#### 8.2.2 Primary Analysis

The primary efficacy endpoint is the average MVPA at Days 7, 14 and 21 as detailed in section 7.4.7.1.

The primary analysis will follow a hierarchical approach as follows:

1. A Mixed Model with Repeated Measures (MMRM) is used to analyse the change from baseline in MVPA average minutes as the response variable with baseline as a fixed effect. Subjects will be included as a random effect, and timepoint will be treated as a

repeated measure within each subject (with compound symmetry structure between visits). If the parameter for the intercept is found to be statistically significant (p-value < 0.05), then the second model below will be used.

2. A Mixed Model with Repeated Measures (MMRM) is used to analyse the change from baseline in MVPA average minutes as the response variable with baseline and timepoint (with unstructured covariance structure between visits) as fixed effects. Adjusted means for each timepoint will be presented along with p-values and 95% confidence intervals (CIs) for the mean change from baseline in MVPA.

Other than the global test for an overall change from baseline (i.e., intercept), there will be no other adjustment for multiplicity. If data are found to be non-normal, the Friedman Test will be used. If the Friedman test is found to be significant then Wilcoxon Signed Rank Pairwise Tests are used for each week comparison.

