### 8.2.3 Secondary Analysis

The following secondary endpoints are analysed in the manner as described for the primary endpoint described in section 8.2.2:

- Change from baseline on Days 7, 14, and 21 in Daily Average number of steps taken.
- Change from baseline on Days 7, 14, and 21 in Ratio of sedentary/non-sedentary time.
- Change from baseline on Days 7, 14, and 21 in Gait, assessed through speed and step irregularity (measured via cadence and gait speed).
- Change from baseline on Days 7, 14, and 21 in Indices of morning stiffness (assessed through levels of mobility 30- and 60-mins post-wake).
- Change from baseline in self-reported pain intensity, assessed through Numeric Rating Scale (NRS) on Days 7, 14 and 21.
- Change from baseline in WOMAC Physical Function subscale on Days 7, 14, and 21.
- Change from baseline in the WOMAC subscales, Pain (composite) and Stiffness (composite) on Days 7, 14, and 21.
- Change from baseline in the WOMAC Global Score on Days 7, 14, and 21.

The secondary endpoint, study subjects' perceived ability to exercise more regularly, assessed using the WOMAC Physical Function subscale on Days 7, 14, and 21, will be analysed by exploring the correlation between WOMAC Physical Function subscale on Days 7, 14, and 21 and the average MVPA as detailed in section 7.4.7.1 (primary endpoint variable) graphically, by means of Spearman rank correlation.

The following secondary endpoints are analysed by descriptive statistics with no formal statistical hypothesis testing performed:

- MVPA on each day of the study (Baseline to final treatment day 21).
- Change from baseline in Karolinska Sleepiness Scale on Days 7, 14, and 21.
- Change from baseline in Health-related quality of life, EQ-5D-5L, on Days 7, 14, and 21.

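### Weekly adjusted means and confidence intervals are planned only if the step 1 test is significant, so a non-significant result has no planned weekly model estimate or interval

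*SAP*

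**What the plan says.** SAP 8.2.2 sets out two steps.

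- **Step 1** is a repeated-measures model for change from baseline in MVPA, "with baseline as a fixed effect" and with compound symmetry between visits. "If the parameter for the intercept is found to be statistically significant" at p < 0.05, "then the second model below will be used".
- **Step 2** adds timepoint, with an unstructured covariance. Only here does the SAP state: "Adjusted means for each timepoint will be presented along with p-values and 95% confidence intervals (CIs) for the mean change from baseline in MVPA".

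If the data are non-normal, a Friedman test replaces the model: "If the Friedman test is found to be significant then Wilcoxon Signed Rank Pairwise Tests are used for each week comparison". No estimate or interval is named for that branch.

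SAP 8.2.3 extends the procedure: "The following secondary endpoints are analysed in the manner as described for the primary endpoint described in section 8.2.2". Counting each variable separately gives 11: steps, sedentary ratio, cadence, gait speed, activity 30 and 60 minutes after waking, NRS, the three WOMAC subscales and WOMAC global.

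Protocol 13.3.1 is similar but not identical. If the intercept is significant, the timepoints "will be added as a fixed effect and adjusted means for each timepoint will be presented". The next sentence says that p-values and 95% intervals "for the mean change from baseline in MVPA will be obtained and presented for each timepoint", and does not repeat the condition.

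SAP 10.6.1 and 10.6.2 tabulate summary statistics by timepoint without any condition, together with the analysis results. SAP 8.1 defines the summaries as mean, SD, minimum, median, maximum and counts. It lists no standard error or confidence interval.

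**The concern.** A pre-specified test may reasonably govern which claims are made. Here it also governs which estimates are produced. The primary endpoint is defined at three weeks, yet if step 1 is not significant the plan calls for no weekly model estimate and no weekly interval. A null result is where a planned interval is most useful, because it shows what size of change the data exclude.

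The same condition is applied separately to each of the 11 secondary variables, so weekly model results would appear for some and not for others, depending on significance. For NRS and WOMAC there is a further loss. SAP 8.2.5.1 relies on the mixed model to deal with missing data, and SAP 3.2.1 assumes 25% dropout. If the condition fails, only observed-case summaries remain for those variables.

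**Working it through.** **Inputs.** Two-sided alpha 0.05, 80% power, standardised effect 0.25, Wilcoxon signed rank test, 147 completers, 25% dropout (SAP 3.2.1, SAP 8.1). The documents give no SD for MVPA change, so results are in units of the SD of the change.

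**1. The plan's own figure.** A one-sample t calculation at d = 0.25 needs 128. Dividing by the minimum asymptotic relative efficiency of the Wilcoxon test gives 128 / 0.864 = 148.1, so about 148. At 147 the power is 79.8%. For dropout, 147 / 0.75 = 196. The stated 147 and 195 are reproduced to within one subject.

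**2. Interval that an unconditional report would give.** The half-width is 1.96 / √n: 1.96 / √147 = 0.16 SD. It is 0.14 at n = 195, and 0.19 at an assumed n = 110 after wear-time exclusions.

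**3. Selection, one-mean approximation.** Treat step 1 as a z-test of one mean at n = 147. With a = d√147:

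- P(significant) = 1 − Φ(1.96 − a) + Φ(−1.96 − a)
- Mean absolute estimate when significant = [a(p₊ − p₋) + φ(1.96 − a) + φ(1.96 + a)] / [(p₊ + p₋)√147], where p₊ and p₋ are the two terms of P(significant)

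| True effect | Not significant | Mean estimate when shown | Ratio |
|---|---|---|---|
| 0.10 | 77% | 0.209 | 2.09 |
| 0.15 | 56% | 0.223 | 1.49 |
| 0.20 | 32% | 0.243 | 1.22 |
| 0.25 | 14% | 0.272 | 1.09 |

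**4. Selection, three-week average.** If step 1 tests the mean of three weeks with an assumed correlation of 0.5 to 0.8, simulation gives ratios of 1.02 to 1.06 at 0.25 and 1.75 to 1.96 at 0.10.

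**5. What the step 1 intercept estimates.** Baseline is a covariate and no centring is stated, so the intercept is the expected change at baseline zero. As an illustration, assume a baseline mean of 2 and SD of 1 (in units of the change SD), one mean, and n = 147. With slope 0 its standard error is √((1 + 2²)/147) = 0.184. A true mean change of 0.25 then gives z = 0.25 / 0.184 = 1.36 and significance about 27% of the time (26% by simulation). For slopes −0.2 and −0.4 the simulated rate is 95% to 100%, and the mean estimates when shown are 0.255 and 0.251, so there is almost no inflation. With zero mean change, slopes 0, −0.2 and −0.4 give significance 5%, 59% and 99.7% of the time. The condition may therefore select on something other than effect size. That is a separate defect, but it means the intercept is not a usable overall estimate.

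**6. What the unconditional tables already hold.** Weekly mean, SD and n allow mean ± t × SD/√n. For the tracker variables SAP 8.2 requires three valid days in every post-baseline week, so each analysed subject contributes all three weeks. With complete data, a common baseline slope and baseline centred at its mean, the generalised least squares equations for the weekly means separate from the slope. The adjusted weekly mean then equals the raw weekly mean. A numerical check with n = 147 and an unstructured covariance gave identical values. This holds only if the summary rows use the same subjects as the model.

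**The case against.** Making week-specific tests conditional on a global test is a legitimate multiplicity device, and several stronger readings fail.

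- **That a null result would carry no precision, or that the sponsor could not say what was excluded.** A reader might infer this. Mean, SD and n are tabulated for every week whatever step 1 shows, so an unadjusted interval can be rebuilt.
- **That the reported effects are selected for being large.** Raw weekly means always appear. For the tracker variables they coincide with the adjusted means under the conditions in step 6 of the working.
- **That only significant inferential results are shown.** Step 1 is run for all 11 secondary variables, and nothing makes its output conditional.
- **That estimates would be about twice too large.** This needs a true effect near 0.10 SD, well below the planned 0.25, and it models a test of one mean, which is not the SAP's step 1.
- **That the protocol already requires weekly intervals.** Its sentence on p-values and intervals can be read that way, and SAP 3.5 declares no departure on this point.
- **That the table shells may include intervals.** They are in a separate document and cannot be checked.

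The first four stand and limit the point. The fifth shows an ambiguity to be reconciled. It does not override the SAP, which places the intervals under step 2 only. Nor does the possible content of unseen shells. What remains is that no weekly model estimate or interval is planned when step 1 is not significant, and that for NRS and WOMAC the raw summaries do not replace the mixed model.

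**Conclusion.** The point holds as a gap in planned reporting. Followed as written, the SAP makes the weekly adjusted means, model p-values and 95% intervals for the primary endpoint and 11 secondary variables depend on a significant step 1 intercept. What is lost otherwise is the planned model-based estimate and its interval. An unadjusted interval remains recoverable.

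The loss is smallest for the tracker variables, where raw and adjusted means should nearly coincide. It is larger for NRS and WOMAC, where the model also carries the missing-data assumption.

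Selection affects the model-based estimates only: about 2% to 9% at 0.25 SD, and 1.75 to 2.1 times at 0.10 SD. These ranges rest on normal approximations at n = 147, on step 1 testing a mean change, and on an assumed between-week correlation of 0.5 to 0.8 for the three-week version. They do not describe the uncentred intercept. Since SAP 3.2.1 says no similar MVPA study existed, a small true effect cannot be ruled out. The change is worth making, though it does not threaten the validity of the trial.

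**What to change.** - Fit the second model whatever step 1 shows. Report weekly adjusted means with 95% intervals for the primary endpoint and every secondary endpoint analysed this way.
- Use the step 1 test only to decide whether week-specific significance is claimed. Its 0.05 level and the order of testing do not change.
- Report the overall adjusted mean change at the mean baseline (baseline centred) with its 95% interval, not the uncentred intercept.
- In the Friedman and Wilcoxon branch, always report a weekly location-shift estimate, such as Hodges-Lehmann, with a 95% interval.
- Reconcile protocol 13.3.1 with SAP 8.2.2 on whether p-values and intervals are conditional.

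The cost is SAP wording and slightly more output. No new data are needed.

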### 3.2.1 Sample Size

Sufficient individuals will be screened to enrol approximately 195 subjects assuming an estimated 25% drop out rate. It is believed that for this study 147 completed subjects are deemed sufficient to observe an improvement in QoL.

There were no previous similar studies measuring MVPA coupled with daily use of a diclofenac gel. Thus, the effect size was chosen based on literature review to detect even mild improvement in QoL factors: “An effect magnitude between 0.2 and 0.5 indicates mild improvement, between 0.5 and 0.8 indicates moderate improvement, and greater than 0.8 indicates considerable improvement in symptoms and QoL.” The sample size was based on a significance level ( $\alpha$ ) = 0.05, Power ( $1-\beta$ ) = 80%, and a standardized effect size of 0.25

Literature review also indicated that QoL scores are not normally distributed. Subjects with worse baseline symptoms showed larger improvement in QoL scores. Therefore, a two-sided non-parametric Wilcoxon Signed Rank test calculation was performed.

Using the above parameters, we obtain a sample size  $N = 195$  to retain the required 147 completed subjects. Therefore, it has been determined that 195 eligible subjects will be recruited for the trial, with an anticipated 147 study subjects expected to successfully complete the study.

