## 8. Analysis Methods

### 8.1 General Methods

Post-Text TLFs are provided in collated electronic PDF files.

For continuous variables, the mean, standard deviation, minimum, median and maximum are presented, together with the total number of observations and the number of missing and non-missing values. Unless otherwise specified, minimum and maximum values are reported to the same number of decimal places as the recorded measurements; mean and median are reported to one more decimal place and standard deviation one additional decimal place more than the mean.

For categorical variables, absolute and relative frequencies are reported. Relative frequencies are based on all observations and reported as percentages to one decimal place. Unless otherwise specified, percentages are based on the number of subjects with data and are not calculated for missing categories.

Adverse events are reported on a per-subject basis, i.e. if a subject reported several events coded to the same coding term the subject is counted only once at the respective level of display. The percentages are calculated using the number of subjects in the population Analysis Set as the denominator.

All hypotheses are tested at a 5% level of significance using a two-sided test unless otherwise specified.

P-values are rounded to three decimal places. If a p-value is less than 0.001 it is reported as "<0.001." If a p-value is greater than 0.999 it is reported as ">0.999.

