#### 8.2.1 Hypothesis and Testing Strategy

The primary and secondary efficacy endpoint analyses aim to demonstrate that there is a difference between baseline and post-baseline in the variable of interest for each endpoint. More formally, the following hypothesis will be tested:

$H_0$ : There is no difference between baseline and post-baseline (Days 7, 14 and 21) in the endpoint of interest.

$H_1$ : There is a difference between baseline and post-baseline (Days 7, 14 and 21) in the endpoint of interest.

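### In the MMRM branch, the step 2 weekly confidence intervals ignore the sampling error of the mean baseline and are somewhat too narrow for the mean change they report

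*SAP*

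**What the plan says.** The null hypothesis in SAP 8.2.1 is: "There is no difference between baseline and post-baseline (Days 7, 14 and 21) in the endpoint of interest". SAP 8.2.2 tests it in two steps. Step 1 is a mixed model for change with baseline as a fixed effect, and its intercept must reach p < 0.05 before step 2 is used. Step 2 again takes change as the "response variable with baseline and timepoint (with unstructured covariance structure between visits) as fixed effects", and its output is specified as: "Adjusted means for each timepoint will be presented along with p-values and 95% confidence intervals (CIs) for the mean change from baseline in MVPA". If the data are non-normal, a Friedman test followed by Wilcoxon signed rank tests replaces the models.

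SAP 8.2.3 extends this to a list of secondary endpoints: "The following secondary endpoints are analysed in the manner as described for the primary endpoint described in section 8.2.2". The list covers steps, sedentary ratio, cadence and gait speed, morning stiffness, NRS and the WOMAC scores.

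Protocol 13.3.1 has no baseline covariate. It tests an intercept, after which timepoint "will be added as a fixed effect and adjusted means for each timepoint will be presented". SAP 3.5 lists only the change to the mITT definition as a departure from the protocol. The SAP does not state the baseline value at which adjusted means are evaluated.

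**The concern.** With no comparator, the adjusted mean is itself the quantity tested against zero. By default it is evaluated at the observed mean baseline of the sample, and its standard error treats that number as a known constant. The mean baseline is in fact an estimate. If the sample happens to start low, regression to the mean lifts the follow-up values even if the gel does nothing, and the model's standard error has no term for this. In a randomised comparison the same error is shared by both arms and largely cancels. Here nothing cancels it.

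At stake are the headline weekly MVPA intervals and p-values, and those of every secondary endpoint that goes through the same model.

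**Working it through.** **Inputs from the documents.** Single arm (SAP 3.2); 147 completers and 195 enrolled (SAP 3.2.1); power and effect size "80%, and a standardized effect size of 0.25"; for the level, "All hypotheses are tested at a 5% level of significance using a two-sided test unless otherwise specified" (SAP 8.1). The correlation rho between baseline and follow-up and the SDs are not given. They are assumed below and shown as a range.

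**The plan's own figure.** SAP 3.2.1 says that "a two-sided non-parametric Wilcoxon Signed Rank test calculation was performed".
- Normal approximation: (1.96 + 0.842)^2 / 0.25^2 = 125.6.
- Divided by the minimum relative efficiency of the signed rank test, 0.864: 146. The t-based version gives 148, with 79.8% power at 147.
- 147 / 0.75 = 196, against 195 stated.

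So 147/195 is reproduced to within rounding. The planning test is a one-sample test on the changes, so its variability is that of the change, not of a residual after adjusting for baseline.

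**The two standard errors.** With complete data the adjusted mean at the sample mean baseline equals the raw mean change. Only the SE differs.
- Correct variance of the mean change: (sY^2 + sB^2 - 2 rho sY sB) / n.
- Variance used by the step 2 model: sY^2 (1 - rho^2) / n.
- With equal SDs the ratio is (1 - rho^2) / (2(1 - rho)) = (1 + rho)/2, so the SE ratio is sqrt((1 + rho)/2).
- Type I error of one weekly test, ignoring the gate: 2 Phi(-1.96 x SE ratio). Coverage is 100% minus this.

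Example at rho 0.5: SE ratio sqrt(0.75) = 0.866; 1.96 x 0.866 = 1.697; type I error 9.0%.

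| Assumed rho | SE ratio | Type I (formula) | Coverage | Type I (simulated, n = 147) |
|---|---|---|---|---|
| 0.3 | 0.806 | 11.4% | 88.6% | 11.1% |
| 0.5 | 0.866 | 9.0% | 91.0% | 8.6-9.4% |
| 0.7 | 0.922 | 7.1% | 92.9% | 6.6-7.3% |
| 0.8 | 0.949 | 6.3% | 93.7% | 6.1-6.8% |
| 0.9 | 0.975 | 5.6% | 94.4% | 5.4-6.0% |

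The simulations fitted a common baseline slope with unstructured covariance over three weeks and no true change, with 8,000 runs per scenario (6,000 at rho 0.3). A paired t-test on the same 8,000-run data rejected 4.5% to 5.5%.

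**MVPA.** The tracker baseline is an average over 3 to 7 days (Protocol 9.2.1), and SAP 8.2 requires at least 3 valid days at baseline and in each weekly period. Assume a stable level per subject plus independent daily noise, with single-day intraclass correlation ICC. The variance of a k-day mean is then between-subject variance + within-subject variance / k.

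Example with ICC 0.5, a 3-day baseline and a 7-day week:
- sB^2 = 0.5 + 0.5/3 = 0.667; sY^2 = 0.5 + 0.5/7 = 0.571; covariance 0.5.
- Variance of change = 0.667 + 0.571 - 1 = 0.238.
- Residual variance = 0.571 - 0.25/0.667 = 0.196.
- SE ratio = sqrt(0.196/0.238) = 0.908; type I error 7.5%.

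Over the range:
- 3-day baseline: 10.3%, 8.6%, 7.5%, 6.7% and 6.1% at ICC 0.3, 0.4, 0.5, 0.6 and 0.7.
- 7-day baseline: 6.7% to 5.3% over the same ICCs.

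**With the step 1 gate.** Same simulations, probability of passing step 1 and then rejecting in a given week:
- Intercept taken at baseline zero, assumed baseline mean/SD of 1.2: step 1 passes in 95% to 100% of null trials for rho 0.5 to 0.8, and the gated weekly rate is 5.2% to 9.4%. At rho 0.9 it is 3.3% to 3.9%. At rho 0.7 with mean/SD 0.5 it is about 3.8%.
- Baseline centred at the sample mean: step 1 has the same SE defect (6.0% to 11.8% instead of 5%), and the gated weekly rate is 3.1% to 6.2% for rho 0.5 to 0.9. The same gate and tests without the covariate give 2.1% to 3.0%.

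**The case against.** - **Conditional inference.** Conditioning on covariates is ordinary regression practice, and the SE is right for subjects whose baseline equals this sample's mean. That is true, but SAP 8.2.1 does not state such a hypothesis and 8.2.2 calls the output the mean change from baseline.
- **Evaluation point.** The SAP does not say where adjusted means are evaluated, and the table shells are in a separate document. This stands: the finding rests on the usual default.
- **The gate.** Step 2 is used only after step 1 is significant. A reader might infer from the table that the trial's type I error exceeds 5%. The documents do not support that: the gated rate falls on either side of 5%, depending on how the intercept is defined, on rho and on the baseline mean/SD. The gate does not repair the intervals, though. Once it opens, for instance because one week has a real effect, they are reported with the short SE.
- **The non-parametric branch.** A reader might also infer that every formally tested secondary endpoint is affected. Friedman and Wilcoxon tests use no adjusted mean, and SAP 3.2.1 expects QoL scores to be non-normal. The problem is therefore confined to endpoints that stay in the MMRM branch.
- **Size.** A doubling of alpha needs rho of about 0.4 or less. No document gives rho, and a narrow baseline spread, as may occur for NRS at entry, reduces the effect. For MVPA the inflation is mostly modest.
- **Value of the covariate.** That it adds nothing holds only for complete data. This is nearly so for tracker endpoints under the wear rule, but not for questionnaires with later readings missing.

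**Conclusion.** The point holds in limited form. If adjusted means are taken at the sample mean baseline, the step 2 intervals are too narrow for the population mean change whenever change correlates with baseline. The direction is certain under that condition; the size is not. With equal SDs and complete data, assumed rho of 0.5, 0.7 and 0.9 gives coverage of about 91%, 93% and 94.4%. For MVPA the ungated weekly type I error is mostly about 5.3% to 8.6%. It passes 10% only with a 3-day baseline and an ICC of 0.3, or for weakly correlated questionnaires. No claim follows about the error rate of the complete gated procedure, and the Friedman/Wilcoxon branch is untouched.

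**What to change.** In SAP 8.2.2 step 2, and for the endpoints that 8.2.3 sends through it, model baseline and Weeks 1, 2 and 3 as four repeated responses, with timepoint as the only fixed effect and unstructured covariance. Report each week-minus-baseline contrast with its p-value and 95% CI. With complete data the point estimates do not change and the SE becomes that of the change. Baseline information is still used when later readings are missing.

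Step 1 must be restated, because this model has no intercept for change. Use the same model and test the average of the three weeks minus baseline.

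The simpler alternative is to drop the baseline covariate from both steps, as in Protocol 13.3.1. That accepts some loss of baseline information where later questionnaires are missing. Either way, record in SAP 3.5 how the chosen model relates to the protocol's.

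The cost is SAP wording and a few lines of SAS, with no new data. The intervals widen by the inverse of the SE ratio: about 15% at rho 0.5, 8% at 0.7 and 3% at 0.9. At n = 147 and rho 0.7 the half-width goes from about 0.150 to 0.163 SD of change. For MVPA the widening is about 1% to 20%, depending on baseline length and ICC.

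### An undefined normality check can replace the primary MMRM of MVPA with rank tests, changing the question and the power without protecting the error rate

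*SAP*

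**What the plan says.** SAP 8.2.2 describes two MMRM steps. The first tests an intercept with baseline in the model. If that is significant, the second gives adjusted means, p-values and 95% CIs by timepoint. The section then states: "If data are found to be non-normal, the Friedman Test will be used". A significant Friedman result leads to pairwise signed-rank tests by week. No estimate or interval is specified on that route.

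Protocol 13.3.1 has the same trigger but leaves the test open: "If data are found to be non-normal, an appropriate non-parametric test will be performed". SAP 8.2.3 extends the rule: "The following secondary endpoints are analysed in the manner as described for the primary endpoint described in section 8.2.2". That covers eight listed items, or 11 variables when cadence and gait speed, the 30- and 60-minute indices, and WOMAC pain and stiffness are counted singly (1 + 1 + 2 + 2 + 1 + 1 + 2 + 1).

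SAP 8.1 fixes the level ("All hypotheses are tested at a 5% level of significance using a two-sided test unless otherwise specified") but says nothing about checking distributions. The sample size rests on a third method: "Therefore, a two-sided non-parametric Wilcoxon Signed Rank test calculation was performed". The reason given is "Literature review also indicated that QoL scores are not normally distributed"; no distribution is given for MVPA.

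**The concern.** The check can only be made once data exist, in an open-label single-arm study. The documents leave open whether raw minutes, changes or residuals are examined, in which week, by which test and cut-off, and who decides. They also leave open whether Friedman compares the three weekly changes or baseline plus three weeks.

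The two routes answer different questions. The MMRM estimates a mean change in minutes. Friedman and the signed-rank test work on ranks. If the check fires, the baseline-adjusted mean changes and their CIs promised in step 2 disappear, and both the hypothesis and the power change with them.

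**Working it through.** **1. The plan's own figure.** Inputs from SAP 3.2.1: two-sided alpha 0.05, "80%, and a standardized effect size of 0.25", signed-rank test, 25% dropout. One-sample size: ((1.960 + 0.842)/0.25)² = 125.6. Dividing by 0.864, the lowest efficiency of the signed-rank test relative to the t-test (my assumption about the method), gives 145.4, so 146. The noncentral-t version is 128/0.864 = 148.1. The stated 147 lies between them. 147/0.75 = 196, against 195 stated. The size is reproduced, and it belongs to neither candidate primary test.

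**2. Simulation inputs (assumed, since the documents give none for MVPA).** n = 147 with complete data; three weekly changes with SD 1; between-week correlation ρ of 0.5 and 0.8; normal, t(5), and gamma shapes with skewness 0.5 and 1; 4,000 runs per setting. The mean test is a one-sample t-test on each subject's average change. The compound-symmetry intercept test reduces to this when there is no baseline covariate.

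**3. Is the switch needed?** With no change, the mean test rejects in 4.3-5.3% across all shapes. A second set-up, with normal and log-normal minutes and correlation 0.6 and 0.8, gives 4.8-5.6%.

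**4. How often would it fire?** This depends on the check chosen.
- Shapiro-Wilk at 0.05 in any week: 12-14% for normal data, 82-90% for skewness 0.5, 94-97% for t(5), 100% for skewness 1.
- The same test on subject means: about 39-64% for t(5) or skewness 0.5.

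**5. Disagreement at 0.25 SD in every week.** The variance of the average change is (1 + 2ρ)/3, which is 0.667 at ρ = 0.5 and 0.867 at ρ = 0.8. The standardized shift is 0.25 × √(147/0.667) = 3.71, or 0.25 × √(147/0.867) = 3.26. Power is Φ(3.71 − 1.96) = 96.0%, or Φ(3.26 − 1.96) = 90.3%. A constant gain does not alter how a subject's three weeks rank, so the three-change Friedman stays at 5%. Treating the two tests as independent, disagreement is 0.960 × 0.95 + 0.040 × 0.05 = 91.4%, or 0.903 × 0.95 + 0.097 × 0.05 = 86.3%. Simulated values:

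| Fallback | Disagreement with mean test |
|---|---|
| Signed-rank on average change | 2-26% |
| Friedman, baseline plus three weeks | 5-84% |
| Friedman, three changes | 86-93% |

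Following the any-week Shapiro-Wilk switch under the non-normal shapes cuts rejection from 90-98% to 5-21% with the three-change Friedman.

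**6. Type I error.** Applied mechanically, the switch to the three-change Friedman rejects in 3.4-5.8% under no change. If either test may be declared primary, independence gives 1 − 0.95² = 9.75%; simulated values are 8.4-10.2% across the two set-ups. The rank tests also target another quantity. With skewed changes and zero mean change, signed-rank rejects in 7-16% (skewness 0.5 to 1), and the four-occasion Friedman in about 41% at skewness 1.

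**7. The baseline term.** Step 1 of SAP 8.2.2 includes baseline, which the simulated mean test omits. With baseline uncentred, the intercept is the expected change at zero baseline MVPA. It rejected in 83-100% of second-set-up runs with no true change. Centred at the sample mean with the ordinary model standard error, it rejected in 7.1-15.5%, because that error treats the mean baseline as known. Check for normal data at correlation 0.6: the variance of mean change is (1 + 2 × 0.6)/3 + 1 − 2 × 0.6 = 0.533, and the residual variance after baseline is 0.733 − 0.36 = 0.373. The standard error is therefore short by a factor √(0.373/0.533) = 0.837, and the error rate is 2(1 − Φ(1.96 × 0.837)) = 10.1%, against 9.8% simulated.

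**The case against.** The MMRM is the stated default, and the fallback and its follow-up tests are named in advance. The rule is conditional: it does not invite the analyst to report whichever test succeeds. That stands, and it limits four stronger readings.

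- **Alpha is doubled.** A reader might infer this from having two candidate tests. The SAP wording is a rule, not a choice, and followed mechanically with the three-change Friedman it held about 5%. The 8-10% needs discretion. The undefined trigger leaves room for that, but nothing shows that it was or will be used.
- **The two tests nearly always conflict.** The 86-93% holds only if Friedman ranks the three changes. The SAP does not fix that layout, and its hypothesis in 8.2.1 compares baseline with post-baseline. With other layouts the range runs from 2% to 84%.
- **The switch is bound to happen.** The documents give no MVPA distribution, and the firing rate moves with the quantity checked. The non-normality mentioned in SAP 3.2.1 concerns QoL scores.
- **Friedman discards subjects with a missing week.** For tracker endpoints SAP 8.2 already requires three valid days at baseline and in every post-baseline week, whichever test is used. The loss could arise only for the questionnaire endpoints.

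Mean change would also still appear descriptively, since SAP 10.6.1 asks for summary statistics by timepoint. What would be lost is the adjusted estimate and its interval.

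**Conclusion.** The point holds in this form: an unspecified, after-the-data check can replace the primary analysis with tests of a different quantity that have no planned estimate or CI, and the same applies to each tested secondary variable. Naming Friedman does not pre-specify the analysis while the rule that selects it is undefined. The switch gives no error-rate protection that a test of mean change needs at about 147 subjects. Its cost is a possible change of question and of power, from small to near-total depending on which fallback is meant. All magnitudes rest on the assumed shapes and correlations and on complete data. The 5% result is shown for mean change without the baseline covariate, not for the intercept test as SAP 8.2.2 words it.

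**What to change.** - Delete the switch from SAP 8.2.2. Make the MMRM of mean change in MVPA minutes the sole primary analysis whatever the distribution, with robust standard errors if wanted.
- Define the global test as the adjusted mean change at the mean baseline (centred baseline, or an LS-mean contrast averaged over the three weeks), not the raw intercept. Its standard error must count the sampling variation of the mean baseline. The simplest way is to run the global test without the covariate, as Protocol 13.3.1 words it; with complete data the estimate is the same.
- Always report a signed-rank test of each subject's average change as a pre-named sensitivity analysis that never replaces the primary result.
- Apply the same rule to the tested endpoints in SAP 8.2.3, and align Protocol 13.3.1 or record the change in SAP 3.5.

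The cost is wording plus one extra output per endpoint, with no new data or subjects. With very heavy tails the mean test gives up a little power to a rank test: 91% against 94% for t(5) at correlation 0.8.
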